1.0 ABBREVIATIONS

ALI	Acute Lung Injury
ARDS	Acute Respiratory Distress Syndrome
CPS1	Carbamoyl-phosphate synthetase 1
AL	Arginine-succinate Lyase
AS	Arginine-succinate Synthase
BMT	Bone Marrow Transplant
CFR	Code of Federal Regulations
CNS	Central Nervous System
CRF	Case Report Form
DC	Discharge
DIC	Disseminated Intravascular Coagulopathy
EBC	Exhaled Breath Condensate
ELISA	Enzyme-linked Immunosorbent Assay
eNOS	Endothelial Nitric Oxide Synthase
FiO ₂	Fraction of Inspired Oxygen
HIPAA	Health Insurance Portability and Accountability Act of 1996
ICF	Informed Consent Form
ICU	Intensive Care Unit
IL-1	Interleukin-1
IL-6	Interleukin-6
IL-8	Interleukin-8
iNOS	Inducible Nitric Oxide Synthase
IRB	Institutional Review Board
IV	Intravenous
L-NMMA	NG-Monomethyl-L-Arginine
MAP	Mean arterial blood pressure
mL	Milliliter
mm Hg	Millimeter of Mercury
NAC	N-Acetyl Cysteine
nNOS	Neuronal Nitric Oxide Synthase
NO	Nitric Oxide
NOS	Nitric Oxide Synthase
NO _x	Nitric Oxide Metabolites
O ₂ ⁻	Superoxide
OTC	Ornithine Transcarbamylase
ROS	Reactive Oxygen Species
SAE	Serious Adverse Event
S/F	SaO ₂ / FiO ₂ ratio
SOFA	Sepsis-related Organ Failure Assessment
TNF	Tumor Necrosis Factor
TNF- α	Tumor Necrosis Factor-alpha
VDI	Vasopressor Dependency Index

2.0 STUDY SUMMARY

Title: Prospective, Randomized, Double-Blind, Placebo-Controlled Phase II Trial of Intravenous L-Citrulline to Delay and Potentially Prevent the Need for Invasive Mechanical Ventilation for Acute Hypoxemic Respiratory Failure in Patients with COVID-19 (SARS-CoV2) Illness.

Objective: To evaluate safety and efficacy of a bolus loading dose and continuous intravenous infusion of L-Citrulline compared to placebo in patients hospitalized with COVID-19 infection (SARS-CoV-2).

Hypothesis: Intravenous L-citrulline administration will safely restore the homeostasis of nitric oxide synthase by increasing both plasma citrulline and arginine levels. We also reason that restoration of citrulline/arginine balance through citrulline administration will safely re-establish homeostasis of NOS, lower oxidative stress, and reduce inflammation, thereby delaying and potentially preventing the need for invasive mechanical ventilation in patients hospitalized with COVID-19 infection (SARS-CoV-2).

Study Design:	
Prospective, randomized, placebo-controlled, double-blind design.
 
 1. Enrollment: approximately 6-9 months 2. Plasma citrulline and arginine levels at day 4 will represent the primary biochemical variable. 3. Vasomotor stability, as measured using a vasopressor dependency index (VDI), through study day 10, will represent the primary safety variable. 4. The length of time from the initiation of the treatment to an intubation event for invasive mechanical ventilation measured in hours will represent the primary clinical outcome. 5. Patients will be followed until hospital discharge for mortality, ICU and hospital lengths of stay, and a requirement for invasive mechanical ventilation and non-invasive mechanical ventilation with high flow nasal cannula or BiPAP as additional clinical endpoints. A further comparison will be performed at D28 and D60 based on telephone follow up for those discharged earlier. 6. Patients will exit the study early (prior to 10 days) if they recover and no longer require oxygen therapy.
Treatment Arms:	
 1. Patients will be randomized to IV Citrulline or placebo 2. Patients will receive an initial bolus of 20 mg/kg (maximum 1500 mg), followed by study infusion of 9 mg/kg per hour (maximum 700mg) for up to 10 days. 3. Patients, healthcare providers, and the sponsor will be blinded to which treatment the patient is receiving. The investigational pharmacy independent pharmacist will be unblinded to the treatment assignment and will deliver the correct infusion to the patient's bedside. 4. The time of initiation of the study drug infusion (either L-Citrulline or placebo will represent time zero. 5. Intravenous Citrulline: Patients randomized the citrulline arm will receive an initial loading bolus of 20 mg/kg (maximum 1500 mg) followed by an infusion of 9 mg/kg per hour (maximum 700 mg) for

	
a maximum of 10 days. The citrulline solution will be prepared as a 5% (50 mg/mL) isotonic solution in 5% dextrose water.
 
6. Placebo: Patients randomized to placebo will receive equal volume bolus and study infusion of 5% dextrose water for a maximum of 10 days.

Sample Size/Statistical Considerations:	
 1. The study will enroll up to 66 patients in a 1:1 ratio. 2. Patients will be analyzed on an intention to treat basis. 3. The primary outcome will be time to intubation event—from the initiation of the treatment until intubation for invasive mechanical ventilation—and will be compared using a log-rank test. 4. Plasma citrulline, arginine, and nitric oxide levels will be measured at 2 and 12 hours post-bolus and on days 2, 4, 6, 8, and 10 and compared using Linear mixed model or repeated measures ANOVA analysis. 5. The vasopressor dependency index (VDI) will be measured for hemodynamics. Worst vasopressor dependency index score over the first 6 days will be compared using ANCOVA analysis with the baseline index as the covariate. 6. SaO₂/FiO₂ or PaO₂/FiO₂ ratio will be utilized to measure the progression of ALI. Worst values from days 0, 2, 4, or 6, 8, or 10 will be compared between groups using repeated measures ANCOVA with the baseline value as the covariate.
Inclusion Criteria:	
 1. Age 18-65 years inclusive. 2. Clinical and laboratory evidence of COVID-19 (SARS-CoV2) infection with an acute hypoxic respiratory illness requiring hospitalization and oxygen therapy. 3. Admitted and transferred to floor without intubation.
Exclusion Criteria:	
 1. Subject unable to provide consent. 2. Patient, surrogate, or physician not committed to full support. 3. Malignant or other irreversible condition and estimated 28-day mortality $\geq 50\%$ 4. Moribund patient not expected to survive 48 hours (as defined by the primary medical team) from the start of study infusion 5. End-stage Liver Disease as defined by Child-Pugh Score > 9 6. Currently enrolled in, or having participated, in another study of an investigational compound within the last 30 days 7. Pregnant female or female who is breastfeeding 8. Allergy to L-citrulline or arginine or any citrulline- or arginine-containing product 9. Patient not otherwise suitable for the study in the opinion of any of the investigators 10. Requirement for intubation and invasive mechanical ventilation prior to study enrollment

Primary Clinical Efficacy Variables:	
The primary clinical efficacy variable is time to intubation event in hours from the start of study infusion.
 
Primary efficacy variables will be evaluated comparing intravenous L-citrulline vs. placebo in separate analyses.

Primary Biochemical Efficacy Variables:	
The primary biochemical efficacy variable is plasma levels of citrulline that are associated with primary and secondary clinical efficacy outcomes. It may serve as a surrogate marker for response.

Primary Safety Variable:	
Primary safety variable is hemodynamic status, specifically worst vasopressor dependency index through day 10.

Secondary Clinical Efficacy Variables:	
 1. All-cause hospital mortality 2. The requirement for intubation and invasive mechanical ventilation 3. Length of non-invasive mechanical ventilation in hours 4. Length of oxygen therapy in hours 5. Length of ICU stay in hours 6. Length of hospital stay in hours 7. Difference in proportion of patients intubated 8. Difference in proportion of patients intubated and on MV 9. Duration of mechanical ventilation from consent & post-infusion
Secondary Biochemical Efficacy Variables:	
 1. Plasma levels of citrulline and arginine at 2 hours, 12 hours, and study days 2, 4, 6, 8, 10. 2. Plasma NOx levels at 2 hours, 12 hours, and study days 2, 4, 6, 8, 10. 3. PK-PD analysis/modeling will enable dose proportionality (dose-response effect) determinations for a follow on confirmatory trial.
Secondary Safety Variables:	
Incidence of reported adverse events to include D28 and D60 in-hospital or telephone follow up

Safety Evaluations:	
In addition to vasopressor dependency index, the following laboratory values will be used for safety assessment at baseline and daily through study day 4 when available.
 
 1. Complete blood count with platelets 2. Basic Metabolic profile, including renal function 3. Liver function tests, including SGOT, SGPT, total bilirubin, and alkaline phosphatase 
Adverse events will be recorded prospectively, including incidences of hypotension, hepatitis (i.e., the elevation of liver enzymes), and injection site reactions.

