APPENDIX B- Protocol Clarification Memo

MEMO TO FILE

DATE: 20 January 2021

STUDY NUMBER: CIT-COVID19-002-01

STUDY TITLE: Prospective, Randomized, Double-Blind, Placebo-Controlled Phase II Trial of Intravenous L-Citrulline to Delay and Potentially Prevent the Need for Invasive Mechanical Ventilation for Acute Hypoxic Respiratory Failure in Patients with COVID-19 (SARS-CoV-2) Illness

Protocol Version/Date: Version 2.0, 08 September 2020

[figure not shown]
RE: Protocol Clarification Memo: Requirements of Arterial Blood Gas (ABG) Timepoint

The diagnostic criteria for acute lung injury (ALI) and ARDS utilize the $\text{PaO}_2/\text{fraction of inspired oxygen (FiO}_2)$ [P/F] ratio measured by arterial blood gas analysis to assess the degree of hypoxemia. We hypothesized that the pulse oximetric saturation (SpO_2)/ FiO_2 (S/F) ratio can be substituted for the P/F ratio in assessing the oxygenation criterion of ALI/ARDS associated with SARS Cov2.

S/F ratios correlate with P/F ratios. S/F ratios of 235 and 315 correlate with P/F ratios of 200 and 300, respectively, for diagnosing and following up patients with ALI and ARDS.

UAMS Standard Of Care (SOC) protocol restricts arterial sample collection for ABGs and hence the need to issue the memo.

The ABG requirement in the protocol is not required but if the data is collected it will be entered into the Clinical Data Base.

DocuSigned by:

12/1/2020
Signer Name: [name]
Signing Reason: I approve this document
Signing Time: 20-Jan-2021 12:29:19 PM PST
[name], MPPM (Hon)
82500763261A481A9B13C5C30307C2EB1
Chief Medical Officer
Asklepion Pharmaceuticals, LLC

20-Jan-2021
Date

Protocol Clarification Memo Version 1.0 dated 20Jan2021 Final

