**Table 3: Covariates**

Independent Variables:	Age is likely to be an independent covariate and the intention is to assess its contribution in two age groups (younger and older) as per protocol.
Dependent Variables:	The outcome variable of interest being reduction in morbidity and mortality outcomes. A fuller list is as per the secondary endpoints above.
Continuous variable:	The study involves markers of respiratory function such as P/F ratios and hemodynamic markers such as VDI that are considered continuous variables and are expected to change with study treatment.

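### Protocol item 6 lets either SaO2/FiO2 or PaO2/FiO2 measure lung-injury progression with no rule for choosing, although the two scales differ by 15 to 35 points, and it counts day 0 as an outcome day

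*Protocol*

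**What the plan says.** Protocol Section 2.0, Sample Size/Statistical Considerations, item 6, states that "SaO₂/FiO₂ or PaO₂/FiO₂ ratio will be utilized to measure the progression of ALI". It continues: "Worst values from days 0, 2, 4, or 6, 8, or 10 will be compared between groups". The method is repeated measures ANCOVA with the baseline value as covariate.

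Appendix B (the blood-gas memo) puts forward as a hypothesis that the saturation-based ratio "can be substituted for the P/F ratio in assessing the oxygenation criterion of ALI/ARDS". It gives the correspondence "S/F ratios of 235 and 315 correlate with P/F ratios of 200 and 300, respectively". It explains that "UAMS Standard Of Care (SOC) protocol restricts arterial sample collection for ABGs", and concludes: "The ABG requirement in the protocol is not required but if the data is collected it will be entered into the Clinical Data Base".

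Appendix A marks the SaO2/FiO2 ratio on days 1 to 11 for everyone, with nothing on day 0 and no hour-0 footnote. PaO2 is also marked as a study procedure on days 1 to 11, while the blood gas itself is marked as standard of care.

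Protocol Section 5.1.2 and the SAP (Study Assessments) both name progression of acute lung injury as an additional efficacy measure. The SAP gives no method for it. Its only reference to either ratio is in Table 3: "The study involves markers of respiratory function such as P/F ratios". Neither ratio appears among the efficacy or safety variables of protocol Section 2.0 or in SAP Tables 1 and 2.

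**The concern.** Two things are left open that should be fixed before the data are seen.

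First, the scale. S/F is scheduled for all patients, but P/F will exist only where a blood gas was taken. No rule covers patients or visits with both ratios, requires baseline and follow-up to share a scale, or converts one to the other. An analyst following item 6 may score some patients or visits on P/F and others on S/F. In the range the memo covers, P/F is the lower number for the same hypoxemia. If blood gases follow ICU care or intubation, the choice of scale depends on the clinical course that the treatment is meant to change.

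Second, day 0. It is listed among the days that supply the outcome, and the baseline value is also the covariate. If day 0 is that baseline, the same reading sits on both sides of the model.

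At stake is whether a between-arm difference in oxygenation, or its absence, can be read as a treatment effect.

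**Working it through.** The documents give no effect size, SD or power for this measure, so there is no design figure to reproduce. The check starts from the memo's paired values.

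**1. Offset between the scales.** At P/F 200: 235 − 200 = 35 points. At P/F 300: 315 − 300 = 15 points. Assuming a straight line through the two pairs, the slope is (315 − 235)/(300 − 200) = 0.8 and the intercept is 235 − 0.8 × 200 = 75. Hence S/F = 75 + 0.8 × P/F, and the offset is 75 − 0.2 × P/F: 25 points at P/F 250 and zero at 375. Values outside 200 to 300 are extrapolation (45 points at P/F 150, −5 at 400).

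**2. Switch of scale within a patient.** A patient with S/F 235 at baseline and P/F 200 later has, by the memo, unchanged hypoxemia but an apparent fall of 35 points. From S/F 315 to P/F 300 the apparent fall is 15.

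**3. Effect on the arm comparison.** With identical true oxygenation, spurious difference = offset × (share scored on P/F in placebo − share in citrulline). If the shares are equal, this is zero.

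The illustration assumes that gases exist only in intubated patients, that P/F is then the ratio used, that time to intubation is exponential, and that there is no death or early exit before day 10 (240 h). The times are 72 h and 156 h from protocol Section 10.4; their ratio, 72/156 = 0.46, is the stated hazard ratio. That section does not say whether they are means or medians, so both are shown.

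| Reading | Placebo intubated by 240 h | Citrulline intubated by 240 h | Difference | × 15 | × 35 |
|---|---|---|---|---|---|
| Medians | 1 − 2^(−240/72) = 0.901 | 1 − 2^(−240/156) = 0.656 | 0.245 | 3.7 | 8.6 |
| Means | 1 − exp(−240/72) = 0.964 | 1 − exp(−240/156) = 0.785 | 0.179 | 2.7 | 6.3 |

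The range is about 3 to 9 points in favour of citrulline.

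**4. What that does to a test.** Take 30 per arm (60 in Section 10.4 at 1:1), two-sided 0.05, and an assumed SD of 40 to 80. With k = difference/(SD × √(2/30)), the rejection rate under no true effect is Φ(k − 1.96) + Φ(−k − 1.96). A 20-point difference in P/F use lies between the two values in step 3; 30 points exceeds both.

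| Difference in P/F use | Offset | Spurious difference | SD 40 | SD 60 | SD 80 |
|---|---|---|---|---|---|
| 0 | any | 0 | 5.0% | 5.0% | 5.0% |
| 20 points | 15 | 3.0 | 6.0% | 5.4% | 5.2% |
| 20 points | 35 | 7.0 | 10.4% | 7.4% | 6.3% |
| 30 points | 15 | 4.5 | 7.2% | 6.0% | 5.5% |
| 30 points | 35 | 10.5 | 17.4% | 10.4% | 8.0% |

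**5. Day 0.** This step takes day 0 to be the baseline.
- Single worst value: a patient who rises from S/F 235 to 315 and one who rises from 235 to 275 both have a worst value of 235, equal to the covariate. The difference in recovery is lost.
- Repeated measures: the listed days are 0, 2, 4, 6, 8 and 10. The day-0 outcome equals the covariate, so it carries no treatment effect. With complete data, equal weights and a constant post-baseline effect Δ, the average over the six days is 5Δ/6 = 0.83Δ.

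**The case against.** The strongest reply is that nothing in the plan says the ratios are pooled. Item 6 says one or the other, and its worst value runs over days, not over the two scales. Appendix B can be read as replacing P/F with S/F, which Appendix A schedules for everyone. This stands to the extent that the defect is a missing rule, not a written instruction to mix. It does not close the gap: the memo presents substitution as a hypothesis and has any collected gases entered, item 6 of version 3.0 still allows either ratio, Appendix A still marks PaO2 daily, and the SAP names only P/F.

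A reader might infer that every patient with a blood gas is scored as sicker under a lower-of-the-two rule. No such rule is written, and on the memo's line P/F stops being the lower number above about 375. A reader might also infer an established bias of 9 to 13 points. That needs medians together with offsets of 35 to 55 (0.245 × 35 = 8.6; 0.245 × 55 = 13.5). The upper offsets are extrapolated beyond the memo's two pairs, and Section 10.4 never calls its times medians; a value equal to its own SD fits an exponential mean at least as well.

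On day 0, it can be said that the phrase about repeated measures means each day's worst value, with day 0 serving only as covariate. That would be a sound model, but item 6 places day 0 among the days compared. Appendix A shows no day-0 ratio at all, so the text needs correcting on any reading.

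Finally, the ratio is not a listed endpoint and the SAP contains no analysis of it. That is true, and it limits the consequence.

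**Conclusion.** The concern holds as a missing rule with a demonstrable cost, not as a proven bias. At equal hypoxemia the memo's values differ by 35 points at P/F 200 and 15 at P/F 300, with P/F lower. Using P/F for some patients or visits makes them look sicker, or appear to worsen, with no change in oxygenation. The arm comparison is biased only if P/F use differs by arm, for example through intubation or ICU care. The documents give no figures on this; equal use adds only noise.

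The illustrative spurious difference of about 3 to 9 points rests on the exponential rates, on gases only in intubated patients, and on offsets within the memo's range. Whether it matters depends on an SD that the documents do not state.

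The day-0 wording is a separate fault, which can make the outcome equal the covariate.

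Both faults affect a supportive measure outside the endpoint lists. The stratified log-rank test for time to intubation uses neither ratio and is unaffected. The change is worth making because the measure is named as efficacy evidence and the remedy is cheap.

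**What to change.** Before database lock:

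- In item 6 and in the SAP, analyse S/F only, since it is scheduled for all patients on days 1 to 11. Alternatively, convert P/F to S/F by one equation stated in advance. Require the same scale at baseline and follow-up.
- Define baseline as the last S/F before the infusion starts. Appendix A does not schedule an hour-0 S/F, so tie the day-1 reading to it. State whether saturation is SaO2 (item 6) or SpO2 (Appendix B).
- Delete day 0 from the outcome days.
- Choose one model: ANCOVA on the worst post-baseline value, or a repeated-measures model on the post-baseline days. A single worst value does not fit a repeated-measures analysis.
- Add this analysis to the SAP, and replace P/F by S/F in SAP Table 3.
- Reconcile the daily PaO2 entries in Appendix A with the memo that makes blood gases optional.

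Cost: edits to both the protocol text and the SAP, and a pre-infusion S/F to be identified for each patient. No new procedure is needed beyond fixing that baseline reading. Under the S/F-only option, P/F values become descriptive only.

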APPENDIX A: Schedule of Events

Measurement	Day 0 (baseline)	Day 1	Day 2	Day 3	Day 4	Day 5	Day 6	Day 7	Day 8	Day 9	Day 10	Day 11	Day 12-DC	Day 28 ^e Follow-up	Day 60 ^e Follow-up
Informed Consent	X														
Demographics- Hx & Px	X														
Eligibility Assessment	X														
Pregnancy Test	Xc														
Study Drug Administration		X	X	X	X	X	X	X	X	X					
Vital Signs		X	X	X	X	X	X	X	X	X	X	X	X		
Mean Arterial Pressure		Xa,b,d	X	X	X	X	X	X	X	X	X	X			
Vasopressor Dosages		Xa,b,d	X	X	X	X	X	X	X	X	X	X			
Basic Metabolic Panel		A	A	A	A	A	A	A	A	A	A	A			
CBC		A	A	A	A	A	A	A	A	A	A	A			
LFTs		Ab	A	A	A	A	A	A	A	A	A	A			
D-dimer blood draw		Xa,b	X		X		X		X		X		X		
CRP		Xa,b	X		X		X		X		X		X		
5 ml blood for citrulline etc.		Xa,b	X		X		X		X		X				
SaO2/ FiO2 ratio		X	X	X	X	X	X	X	X	X	X	X			
PaO2		X	X	X	X	X	X	X	X	X	X	X			
ABG		A	A	A	A	A	A	A	A	A	A	A			
Hospital status		X	X	X	X	X	X	X	X	X	X	X	X	X	X
ICU status		X	X	X	X	X	X	X	X	X	X	X	X	X	X
Non-invasive ventilation status		X	X	X	X	X	X	X	X	X	X	X			
Invasive ventilation status		X	X	X	X	X	X	X	X	X	X	X			
ConMed Review		X	X	X	X	X	X	X	X	X	X	X	X	X	X

Adverse Event Review		X	X	X	X	X	X	X	X	X	X	X	X	X	X	X
----------------------	--	---	---	---	---	---	---	---	---	---	---	---	---	---	---	---

a= measurement should be recorded or performed at hours 0, 2 and 12

b= Day 1 hour 0 samples/procedure must be collected/recorded before study drug is administered.

c= only perform if patient is of childbearing potential

d= must be collected 15 minutes prior to administration of study medication

e= Day 28 and Day 60 are telephone follow ups

X= Study Procedure A= Standard of Care

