## **STUDY ASSESSMENTS**

The assessment of efficacy will include collection of plasma for analysis of citrulline and arginine levels at 2 hours, 12 hours, and the alternating morning of study days the infusion is running for a maximum of

10 days, i.e., on days 2, 4, 6, 8 and 10. A patient will exit the study early if they have been weaned off all oxygen support before 10 days. Additional efficacy measures will include clinical outcomes, including progression of acute lung injury and lengths of hospital and ICU stay.

The assessment of safety will include collection of hemodynamic measurements at least every 4 hours on a hospital unit and--if a patient is critically ill in an ICU--hourly while the study material is infusing and for 12 hours after completion of the infusion in each patient. Hemodynamic measurements will be converted to a vasopressor dependency index for analysis if a patient becomes critically ill. Adverse event reporting will also serve as a means of safety analysis. Additional safety measures will be biochemical and hematologic laboratory measurements. The biochemical laboratory measurements, including liver function tests (ALT, AST, bilirubin, alkaline phosphatase), kidney function tests, D-dimer tests, CRP and electrolytes, along with hematologic laboratory measurements, including complete blood count and platelet count, will be collected when available for any study day in order to evaluate for adverse events.

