## **SAMPLE SIZE**

This study will accrue approximately 66 patients in a 1:1 fashion to account for 10% attrition. This sample size was determined on the basis of an expected time to intubation event in the placebo group derived from historical data on critically ill patients with COVID-19 infection (SARS-CoV-2) of 3 days (72 hours) +/- 3 days (72 hours). An acceptable effect size in the intravenous citrulline group would be delay in time to an intubation event of at least 6.5 days (156 hours). Thus, a two-sided log-rank test with an overall sample size of 60 patients achieves 81% power at a 0.05 significance level to detect a hazard ratio of 0.46 when the placebo group time to intubation is 3 days. The study is expected to last 12 months, of which patient accrual will occur in the first 6-9 months. The accrual pattern across time is uniform.

In terms of mortality, in patients who progress to acute hypoxic respiratory failure requiring ICU care, the mortality is 50%. With a sample size of 60 patients, the study will have 80% power to detect a difference between the group proportions of -33%. The mortality in the intravenous citrulline group is assumed to be 50% under the null hypothesis and 17% under the alternative hypothesis. Again, the mortality rate for the placebo group is assumed to be 50%. The test statistic used is the two-sided z-test with pooled variance with a 0.05 significance level.

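### The oxygenation analysis uses even days only although the ratio is scheduled daily, lists day 0 as both outcome and baseline, and is not defined in the SAP (minor)

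*Protocol*

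**What the plan says.** Protocol section 2.0, Sample Size/Statistical Considerations, item 6, states that the SaO2/FiO2 or PaO2/FiO2 "ratio will be utilized to measure the progression of ALI". The rule is: "Worst values from days 0, 2, 4, or 6, 8, or 10 will be compared between groups using repeated measures ANCOVA". The patient's baseline ratio is to enter that model as a covariate.

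The row "SaO2/ FiO2 ratio" in Appendix A is marked X on each of days 1 to 11. It is blank on day 0 and from day 12 to discharge. The key reads "X= Study Procedure A= Standard of Care", so these are protocol measurements and do not depend on routine care. PaO2 is also marked X on days 1 to 11, but the memo in Appendix B relaxes blood gases: "The ABG requirement in the protocol is not required but if the data is collected it will be entered into the Clinical Data Base". SaO2/FiO2 is therefore the measure that can be expected every day.

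Protocol section 10 does not repeat the analysis. In the SAP, Study Assessments says: "Additional efficacy measures will include clinical outcomes, including progression of acute lung injury and lengths of hospital and ICU stay". Table 3 mentions P/F ratios as a continuous variable. Neither place gives days, a summary measure or a model. Protocol section 10.2 leaves the detailed methods to the SAP.

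**The concern.** Days 2, 4, 6, 8 and 10 are the blood-sampling days of item 4. Alternate days are understandable for blood draws. They are harder to explain for a bedside ratio recorded daily, and no explanation is offered. A rule built on worst values benefits from every reading available, because the lowest of a subset can never be below the lowest of the full set.

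Two further defects sit in the same sentence. Day 0 appears among the outcome days although baseline is the covariate, so one value could be used on both sides of the model. The sentence also combines worst values with a repeated measures method and does not say whether worst means within each day or over the whole course. Because the SAP does not take the analysis up, nothing resolves these questions before the data are seen. At stake are some precision in the only planned comparison of oxygenation, and freedom to choose its definition afterwards.

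**Working it through.** The documents give no power, variance or nadir rate for this analysis, so there is no plan figure to reproduce.

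**1. Share of scheduled values not used** (Appendix A against item 6)

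- Days 1-10: 10 scheduled, 5 used, 5/10 = 50% unused.
- Days 1-11: 11 scheduled, 5 used, 6/11 = 55% unused.
- Days 2-10 (the day 1 reading is the baseline): 9 scheduled, 5 used, 4/9 = 44% unused.
- Days 2-11: 10 scheduled, 5 used, 5/10 = 50% unused.

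**2. Which value is day 0?** Protocol section 7.2.2 sets time zero at the start of infusion, and Appendix A places hour 0 on Day 1. The ratio row has no day 0 mark, and its Day 1 mark lacks the hour-0 and pre-dose footnotes that the MAP row carries. The schedule does not say whether the day 1 ratio precedes or follows the start of infusion.

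**3. What the odd days would add.** Assumptions, none from the documents: between-patient SD 40, within-patient SD 50, day-to-day correlation 0.5, 0.7 or 0.85, reading error SD 0 or 25, and a constant 32-point shift from day 1 on. There are 30 patients per arm (60/2), flat courses, and no early exit. The residual SD is SD(y) × sqrt(1 - r²), where r is the correlation of the summary y with baseline. Power is for a two-sided 5% comparison of two means. Repeated measures is approximated by the mean over days. The baseline is the day before day 1.

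| Correlation / error SD | Worst: even | Worst: days 1-10 | Mean: even | Mean: days 1-10 |
|---|---|---|---|---|
| 0.5 / 0 | 75.3% | 79.4% | 86.4% | 89.9% |
| 0.5 / 25 | 68.3% | 73.1% | 81.7% | 86.4% |
| 0.7 / 0 | 76.3% | 80.5% | 84.9% | 88.3% |
| 0.7 / 25 | 68.5% | 73.1% | 79.5% | 83.9% |
| 0.85 / 0 | 83.3% | 87.3% | 88.4% | 91.5% |
| 0.85 / 25 | 72.8% | 77.3% | 81.1% | 85.3% |

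- One worst value per patient: gain 4.0 to 4.8 points.
- Repeated values: gain 3.1 (91.5 - 88.4) to 4.7 (86.4 - 81.7) points.
- All-day single worst against even-day repeated values: the single worst is lower in every row, by 1.1 (88.4 - 87.3) to 8.6 (81.7 - 73.1) points.

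**4. How much depends on day 1.** Take the day 1 reading as the baseline and compare days 2-10 with the even days in the same model. The change is then between -1.5 and +1.7 points over the six settings and both summaries. The 3-5 points come mainly from having a post-infusion day 1 value close to baseline with the full effect present. A simple mean also weights days equally, which need not be efficient.

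**The case against.** The strongest reply is that the loss is small and the endpoint is peripheral. The comparison appears in neither the primary nor the secondary lists, the sample size does not depend on it, and the even-day rule applies equally to both arms, so no bias between arms is shown. All of that stands and sets the priority.

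Three stronger readings are tempting, but the documents do not support them.

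- **A reader might infer that about half of all nadirs are missed.** No passage says when nadirs occur. In simulated daily series with correlation 0 to 0.95, the lowest post-baseline value falls on an unused day in 50% of patients if courses are flat. The share ranges from 16% (worsening) to 84% (improving). Missing the nadir day also loses little when days are correlated: with flat courses the even-day worst value correlates 0.95 to 0.99 with the all-day worst at correlations of 0.8 to 0.95.
- **A reader might link the odd days to intubation**, since the sample size is set "to detect a hazard ratio of 0.46 when the placebo group time to intubation is 3 days". Intubation does not end the series: the ratio and the invasive ventilation status are both scheduled through day 11. With hour 0 on Day 1, 72 hours falls at the boundary of Days 3 and 4, and Day 4 is a scored day. Shares of intubations on odd days do not count lost readings.
- **A reader might want one overall worst value per patient in place of repeated measures.** The plural values and the named method suggest several values per patient. In the table above, the single worst value over all days has lower power than even-day repeated values in all six settings.

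Under the within-day reading no overall nadir is sought, but the odd days are still unused.

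**Conclusion.** The point holds as a minor one. Item 6 leaves out 44-55% of the scheduled post-baseline ratios without a stated reason, treats day 0 as an outcome and (as baseline) a covariate although the schedule has no day 0 ratio, and leaves the meaning of worst open. The SAP supplies nothing in its place. This follows from the text alone.

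The size of the statistical gain does not follow from the text. About 3-5 power points is what the assumed SDs, correlations and 32-point shift give under either meaning of worst, if a post-infusion day 1 reading exists and the effect is already full on that day. If day 1 serves only as baseline, the gain is about zero. The firmer reasons to act are that the values are already scheduled and that the analysis should be fixed in writing before database lock.

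**What to change.** Amend item 6 and carry the same rule into the SAP before database lock:

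- Use every scheduled post-baseline day through day 10 in the planned baseline-adjusted repeated measures analysis.
- Use the pre-infusion value (Day 1 hour 0) as covariate only, and remove day 0 from the outcome days. State whether the Day 1 ratio in Appendix A is taken before or after the start of infusion. Let it enter as an outcome only if it is a separate reading taken after the start.
- State whether worst means the worst value within each day or over the whole course. Keep the repeated measures method, and do not replace it with one worst value per patient.
- Name SaO2/FiO2 as the daily measure, and say how PaO2/FiO2 is used when a blood gas happens to be available.

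The cost is a few lines of wording. No new assessments are needed beyond confirming that a pre-infusion ratio is recorded, and the sample size is unaffected.
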